Official Study Title: Durability of Combination Therapy With
Exenatide/Pioglitazone/Metformin vs. Conventional Therapy in New Onset
T2DM

NCT number: NCT01107717

IRB Approval Date: 12.04.2019

Unique Protocol ID: HSC20080456H

[Click here for a complete set of instructions for this form.](#)

If an item does not apply to your research project, simply indicate that the question is "**not applicable**."

For the following Sections: 1. "Purpose and Objectives"; 3. "Study Design"; and 4. "Study Population," and 5 – 12, you may copy and paste the relevant passages from the sponsor's full protocol or grant application (only citing the page number and section **will not** be acceptable).

For Section 2, "Background" you may cite the relevant passages (page number and section) from the sponsor's full protocol or grant application.

Click once on the highlighted entry in each box to provide your response. Click the item number/letter for detailed instructions for that question. If your response requires inserting a table, picture, etc, you will need to first delete the box that surrounds the answer and then insert your table or other special document.

1. Purpose and objectives.

List your purpose and objectives:

We hypothesize that initiation of combination therapy at the time of initial diagnosis of type 2 diabetes with antihyperglycemic drugs (pioglitazone, metformin, and exenatide) that specifically target known pathogenic defects (insulin resistance and beta cell dysfunction) responsible for impaired glucose homeostasis will achieve superior and more durable glycemic control and more effectively reduce cardiovascular risk factors compared to the stepwise approach currently recommended by the American Diabetes Association (ADA) and European Association for the Study of Diabetes (EASD).

Specifically, We will test the effect of initiating therapy in newly diagnosed type 2 diabetic subjects with combination pioglitazone/metformin/exenatide therapy compared to the ADA recommended approach (start with metformin and add a second or third oral agent, and then proceed to insulin) on:

- 1) Achievement and maintenance of glycemic control (HbA_{1c} <6.5%)
- 2) Reduction in whole body (muscle) insulin resistance and improvement in beta cell function.
- 3) Improvement in cardiovascular risk factors
- 4) Decrease in carotid intima media thickness, a surrogate measure of atherosclerosis

2. Background.

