No previous study has evaluated the efficacy and durability of combined pharmacological therapy at the time of diagnosis of diabetes with drugs that preserve beta cell function. Furthermore, no previous study has achieved the recommended goal of glycemic control (HbA_{1c} <6.5%) as its primary outcome. In this study we will initiate therapy in subjects with type 2 diabetes at the time of diagnosis with triple therapy (pioglitazone, metformin, exenatide). Pioglitazone and exenatide both exert effects to preserve beta cell function, while pioglitazone, and metformin to a lesser extent, are excellent sensitizers. All three drugs effectively reduce the HbA_{1c} and have beneficial cardiovascular actions. The primary outcome variable is the achievement and maintenance of the recommended target for glycemic control (HbA_{1c} <6.5%) in subjects with type 2 diabetes. We will compare the efficacy of two therapeutic regimens: (i) triple therapy (pioglitazone, metformin, exenatide) at the time of diagnosis of T2DM versus (ii) stepwise therapy starting with metformin and subsequent addition of sulfonylurea and basal insulin (i.e., the "standard" approach) in achieving this goal. The first intervention is based on the novel concept of initiating therapy at the time of diagnosis with combination therapy using agents that correct specific pathophysiologic defects that are characteristic of T2DM (insulin resistance and beta cell failure). The second intervention is based upon stepwise addition of antidiabetic agents to reduce the HbA_{1c} according to the current ADA therapeutic recommendation.

3. Study Design.

Describe the study design (e.g., single/double blind, parallel, crossover, etc.) Consider inserting a scheme to visually present the study design.

Research Design and Methods

Subjects:

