
During visit 1 all subjects will be interviewed by [name] or one of the co-investigators, who will describe in detail the purpose, nature and potential risks of the study. Each subject is then asked to read the consent form. Subjects then will be asked if they have any questions concerning any aspect of the study. All questions will be answered thoroughly and candidly by [name] or one of the co-investigators. Immediately prior to the study, subjects are asked to sign the consent form and are given a photocopy to keep for themselves. The consent forms will be kept in room at TDI.
 
The quality and content of the consent process will be monitored throughout the study period and any changes will be communicated to IRB and the GAC.
	
(8)	
Consent Process Describe the timing of obtaining informed consent, whether there is any waiting period between informing the prospective subject and obtaining consent. (e.g., take consent home, waiting period of X hours, after consulting with family members, etc.)

Subjects will be consented at the first visit, there will be no waiting period.
	
(9)	
Describe measures taken to minimize the possibility of coercion or undue influence during consent.

The study procedures will be explained for the subjects via the phone during the initial contact. They will be encouraged to consult their primary care doctors about their participation in the study. It will be explained to them that their participation in the study is voluntary and there is no penalty for not participating in the study.
	
(10)	
Will subjects from this population be assigned to different research groups?
 
 Yes  No

If yes, list the groups using a short descriptive label. E.g., experimental group A, B, etc., control group, etc. (this information is needed later in the Risk: Benefit Analysis section)
 
[Group I: Combination therapy; Group II: Conventional therapy]
	

5. Informed Consent for Research Involving Non-English Speaking Subjects

A	Individuals who do not speak English will not be enrolled.	
		There is no expected benefit for those participating. (Skip B, and (1) and (2) below this table and go to #6)
B. X	Individuals who do not speak English will be enrolled. The foreign language translation of the consent will be submitted to the IRB:	

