- 7) **EUGLYCEMIC INSULIN CLAMP** On a separate day, subjects will be admitted to the CRC 6:45 and 8 AM for a four-hour, two-step hyperinsulinemic euglycemic insulin (20 and $80 \text{ mU/m}^2 \cdot \text{min}$) clamp with a prime-continuous infusion of $3\text{-}^3\text{H}\text{-glucose}$. The $3\text{-}^3\text{H}$ glucose prime will be $25 \mu\text{Ci} \times$ (fasting plasma glucose/100); the continuous infusion will be given at the rate of $0.40 \mu\text{Ci/min}$ for 240 minutes. Plasma samples for tritiated glucose will be obtained at 5-15 minute intervals during the 30 minutes before and throughout the insulin clamp, to quantitate rates of whole body glucose disposal and suppression of endogenous (primarily hepatic) glucose production. Continuous indirect calorimetry (Deltatrac, Sensormedics, Anaheim, CA) will be performed for 30 minutes prior to the start of the insulin clamp, and during the 210-240 period of

the insulin clamp to calculate rates of glucose and lipid oxidation Total blood loss for the procedure is up to 160 ml.

8) **Fundus Examination:** All diabetic subjects seen at the Texas Diabetes Institute have an annual ophthalmologic examination as part of their routine care. The fundus photographs will be read blindly by University of Wisconsin-Madison, Department of Ophthalmology and Visual Sciences.

Following completion of these tests, subjects will be randomized (using a table of random numbers) to receive, in open label fashion, one of the following treatment regimens:

GROUP I: Group I will be started on pioglitazone (15 mg/day) plus metformin (1000 mg/day) with the supper meal and exenatide (5 mcg s.c. bid 30 min before breakfast and supper).

If, after month one, the FPG ≥ 110 mg/dl or HbA_{1C} $\geq 6.0\%$, the exenatide dose will be increased to 10 mcg bid, pioglitazone will be increased to 30 mg/day, and metformin to 1000 mg bid.

If, after month two, the FPG ≥ 110 mg/dl or HbA_{1C} $\geq 6.0\%$, pioglitazone will be increased to 45 mg/day. Subjects who will not tolerate 5 mg bid exenatide because of GI side effects will be started on lower dose (1 mg s.c bid 30 min before breakfast and supper): and the dose will be titrated up to the maximal tolerated dose.

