If, after month six, the HbA_{1C} $> 6.0\%$, and the subject is on maximum doses of metformin, glipizide, and glargine insulin, the subject will be considered a treatment failure. Regular insulin will be added to each meal when the HbA_{1C} rises to $> 6.5\%$ and adjusted based upon the pre- and post-meal blood glucose levels. These "treatment failure" subjects will continue with all follow up visits/procedures.

Throughout the titration process, downward adjustments will be allowed for the development of hypoglycemia, as defined by a blood glucose less than 60 mg/dl with (symptomatic hypoglycemia) or without (asymptomatic hypoglycemia) symptoms. Serious hypoglycemia is defined as any hypoglycemic reaction requiring assistance from a third party for recovery.

Following their enrollment into the study, all T2DM participants will return to the Clinical Research Center (CRC) at the TDI for follow up visits every 3 months. Telephone calls also will be made to each participant every 6 weeks. During the telephone/CRC visits, subjects will be asked questions about interim medical history, home glucose monitoring results, and compliance with the medical regimen.

During each 3-month follow-up visit to the CRC, body weight, waist circumference (Gulick III tape measure), and blood pressure (Dynamap) will be measured. Blood will be drawn for FPG and HbA_{1c}, and pharmacological therapy will be adjusted based on the HbA_{1c}, FPG, and HBGM results (see prior algorithm). Plasma lipids and 24-hour urine albumin excretion will be measured annually or more frequently as indicated by test results. In addition to glycemic control, all subjects will receive therapy for any abnormal cardiovascular risk factors: hypercholesterolemia (goal LDL <100 mg/dl), hypertriglyceridemia (goal <150 mg/dl), hypertension (goal <130/80 monthly), albumin excretion (goal < 30 mg/day). At the end of three years, the OGTT, DEXA, fundus photography, 24 hour urine for albumin, hyperglycemic clamp, ankle-arm blood pressure, and carotid IMT will be repeated.

Primary End Point: The primary end point of the study is the difference in HbA_{1c} between Group I (triple combination therapy at time of initial diagnosis) and Group II (stepwise therapy).

Secondary End Points: The following parameters will be measured as secondary endpoints;

- 1) Number of subjects in each group with HbA_{1c} < 6.0%

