- 2) Number of treatment failures in each group as defined by HbA_{1c} >6.0% and requiring the addition of rapid acting insulin with meals
- 3) Change in beta cell function
- 4) Change in whole body insulin resistance
- 5) Incidence of hypoglycemia (asymptomatic, symptomatic, serious)
- 6) Change in body weight, total body fat, and waist circumference
- 7) Change in carotid intima media thickness
- 8) Change in ankle-arm blood pressure
- 9) Change in stage of diabetic retinopathy

Change in GFR and urinary albumin secretion rate

Subjects who will complete 3-year follow-up and the repeat studies will continue to receive therapy as described above and continue in the follow-up visit every 3 months as previously described until the last subjects recruited to the study has completed 2-year follow-up. During this follow up period we will repeat the OGTT, eye photographs, DEXA and carotid ultrasound every other year (Year 3 and 6).

Washout Phase

At 6 years, all baseline studies will be repeated as stated above (OGTT, annual labs, eye photographs, ankle-arm blood pressure and carotid ultrasound). After the completion of the repeat studies, hepatic fat content and liver fibrosis will be measured with fibroscan and MRI Spectroscopy.

MRI Spectroscopy is the gold standard method to quantitate hepatic fat content. Pharmacologic therapy will be stopped if participants HbA1C is less than 7.5%. Participants with HbA1C greater than 7.5% and in the triple therapy arm, dapagliflozin (10mg/day) will be added. Participants with HbA1C greater than 7.5% in the conventional therapy arm will be switched to triple therapy. Patients will be seen every 3 months for a follow-up visit. Medical history, physical exam, body weight, blood pressure, Fasting blood sugar and HbA1c will be measured at each follow-up visit. The OGTT will be repeated at 3 months and every 6 months thereafter. Liver fat content and liver fibrosis will be measured with fibroscan annually. The 3-month follow-up visits will continue for additional 5 years, to obtain information about the long-term durability of triple therapy. Liver fat content and liver fibrosis will be measured with fibroscan and MRI annually, and the OGTT will be repeated every 2 years, and all baseline measurements will be repeated at 5 years.

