
Less likely
 
These risks are expected to occur in 5 - 20 [or insert different range] subjects or less out of 100 subjects.
	
 • Abdominal pain (metformin) • Headache (pioglitazone) • Flatulence (pioglitazone) • Vomiting (exenatide metformin) 
Hypoglycemia (glyburide) with a sulfonylurea)
 
Hypoglycemia (with metformin and a sulfonylurea)
 
 • Diarrhea (metformin, exenatide) 
At least 1, but fewer than 10 patients out of 100 patients reported:
 
 • Injection site events (for example: bruising, bleeding, pain, itching, redness of skin, swelling and/or small lump where Exenatide was injected) 
Dyspepsia
 
Gastroesophageal reflux disease
 
Nasopharyngitis
 
Asthenia
 
Feeling Jittery
 
Decreased appetite
 
Dizziness
 
Hyperhidrosis
 
Fewer than 1 out of 100 patients reported:
 
 • Stomach swelling • Stomach pain • Constipation • Gas • Burping • Abnormal taste sensation 	
 • none
		Serious

Rare
 
These risks are expected to occur in less than 1 subjects out of 100
	
Hypoglycemia
 
Fewer than 1 out of 1000 patients reported:
 
 • Sleepiness • Itching • Hives • Spotty/patchy or swollen rash • Rapid swelling of the tissues around the neck, face, mouth, and/or throat indicating an allergic reaction • Hair loss • Dehydration (the loss of too much water from the body), because of nausea, vomiting, and/or diarrhea • Worsening kidney function • Inflammation of the pancreas 
Fewer than 1 out of 10,000 patients reported:
 
 • Hives/itching with difficulty breathing and/or low blood pressure, indicating a severe allergic (anaphylactic) reaction • Thrombocytopenia- a condition in which you have a low blood platelet count. 	
Heart failure (pioglitazone)
 
Bone fracture (pioglitazone)

---	---	---

Are all groups exposed to the risks listed above? Yes No N/A (There is only one group)
 If No, Describe: [Describe here]

Procedure or component 9 Pharmacological therapy, metformin, glyburide/Glipizide and insulin		

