4. The timeliness and accuracy of all information documented in any form and/or records pertaining to the study will be maintained.
5. blood sugar level will be measured every 5 minutes during the clamp to prevent the risk for hypoglycemia

6. following the initiation of therapy subjects will be contacted via phone calls every two weeks to ensure that no serious side effects have happened.
7. Subjects will be examined during the follow-up (every 1-3 months) for potential side effects and for the quality of their blood sugar control. If severe side effects appear, drug dose will be adjusted accordingly. If blood glucose is not adequately controlled, therapy will be adjusted accordingly. Subjects who will receive full dose therapy in either study arm and their A1c remains > 8% will be considered treatment failure and will be returned to their doctor for their standard care.
8. During the euglycemic clamp blood sugar will be tested every 5 minutes and glucose infusion will be adjusted accordingly to maintain blood sugar at target and prevent hypoglycemia.

(2) Where appropriate, discuss provisions for ensuring necessary medical or professional intervention in the event of adverse events, or unanticipated problems involving subjects.

If hypoglycemia during the clamp occurs, the study will be stopped and 20% glucose infusion will be started until plasma glucose concentration is stabilized

(3) Will the safeguards be different between/among groups? Yes No

[If yes, describe here]

8. Available Alternative.

(1) Describe alternative treatments and procedures that might be advantageous to the subjects, should they choose not to participate in the study. This should include a discussion of the current standard of care treatment(s). In some cases the only alternative may be not to participate in the study. This section should match the alternative section of the CF (though not written in second person like the ICF).

although all drugs used in this study are approved by the FDA for lowering blood sugar and group I will be treated according to the ADA recommendations, the participation of patients in this study is completely voluntary. Subjects can choose not to participate in the study and be treated with other combination of currently approved drugs or other drugs not used in this study (acarbose, DPP 1V inhibitors).

9. Confidentiality.

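### The alternatives and risk sections of the IRB form contradict the protocol's own regimens, procedures and endpoints in five places

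*Combined protocol and SAP*

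**What the plan says.** **Which arm is the guideline arm.** Section 8 (Available Alternative) says that "group I will be treated according to the ADA recommendations". Section 4, item (10), labels the arms "Group I: Combination therapy; Group II: Conventional therapy". Section 1 describes the experimental regimen as "compared to the ADA recommended approach (start with metformin and add a second or third oral agent, and then proceed to insulin". The last paragraph of Section 2 says: "The second intervention is based upon stepwise addition of antidiabetic agents to reduce the HbA_{1c} according to the current ADA therapeutic recommendation". The Abstract calls triple therapy at diagnosis the novel approach and stepwise therapy the ADA-recommended one.

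**Group II risks.** The Section 6c table for metformin, glyburide/glipizide and insulin (component 9) names Group II only. Hypoglycemia appears once, as likely and not serious. The serious cell reads none in all three frequency rows. Section 6a, under both groups, states: "Serious hypoglycemia is defined as any hypoglycemic reaction requiring assistance from a third party for recovery". Secondary endpoint 5 counts asymptomatic, symptomatic and serious hypoglycemia.

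**Group I risks.** Section 6a: "Group I will be started on pioglitazone (15 mg/day) plus metformin (1000 mg/day) with the supper meal and exenatide". After month six, glargine and then mealtime regular insulin can be added. The component 8 table names Group I only. In its row for 5 to 20 per 100 it lists "Hypoglycemia (with metformin and a sulfonylurea" and a second sulfonylurea entry that names glyburide. It does not mention insulin.

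**Euglycemic clamp.** Section 6a, item 7, gives a primed continuous infusion of tritiated glucose. The component 6 table lists hypoglycemia, local reactions and blood loss.

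**Year 6.** Under Washout Phase, therapy stops below an HbA1c of 7.5%. Above it, for the triple-therapy arm, "dapagliflozin (10mg/day) will be added", and conventional-arm participants switch to triple therapy.

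**The concern.** Section 6c asks for a risk-benefit table for each procedure in Section 6b. The note to Section 7 asks, as a minimum, for safeguards against the serious risks listed before it. The form's instruction for Section 8 says that it should match the alternatives section of the consent form. These parts therefore feed the IRB's judgment and the consent wording.

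If they describe the wrong arm or the wrong drugs, the IRB weighs risks that do not belong to the treatments given. A reader of Section 8 would take the experimental combination for guideline care. A reader of component 9 would conclude that sulfonylurea plus insulin carries no serious risk, while the same protocol plans to count a serious event on that treatment.

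**Working it through.** The first three items and the fifth are comparisons of text. Only the tracer involves arithmetic. The plan states no total for the tracer, so there is no figure to reproduce.

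1. **Arm label.** Section 8 gives ADA care to Group I. Sections 1 and 2 and the Abstract give it to the stepwise arm, and Section 4 labels Group II conventional. No passage outside Section 8 makes Group I the ADA arm.

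2. **Component 9 against Section 6a.** The table puts hypoglycemia in its highest frequency band (more than 20 per 100) but only as not serious. The form asks for rare and serious events as well as expected ones. An event that the protocol defines under Group II and counts as an endpoint is reasonably foreseeable, so an entry of none in all three serious cells conflicts with Section 6a. The cells are filled and legible, so this is not a gap left by redaction or text extraction. Section 7(2), on intervention in adverse events, covers only hypoglycemia during a clamp.

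3. **Component 8 against Section 6a.**
   - Sulfonylurea steps for Group I in Sections 3 and 6a: none. Sulfonylurea entries in the table: two.
   - Insulin steps for Group I in Section 6a: glargine up to 60 units, then mealtime regular insulin. Insulin entries in the table: none.
   - Hypoglycemia with no drug named appears only in the rare row, outside the cell that holds heart failure and bone fracture.
   - The table names Group I only, but the year-6 switch exposes some Group II participants to the same drugs.

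4. **Tracer in component 6.** Inputs from Section 6a, item 7: prime 25 microcuries × (fasting plasma glucose/100); infusion 0.40 microcuries/min for 240 minutes. The fasting glucose is an assumption of 100 to 200 mg/dl.
   - Infusion: 0.40 × 240 = 96 microcuries.
   - Prime at 100 mg/dl: 25 × 1 = 25. Total 25 + 96 = **121 microcuries**.
   - Prime at 200 mg/dl: 25 × 2 = 50. Total 50 + 96 = **146 microcuries**.
   - Section 6b and the clamp payment schedule in Section 10 give two such clamps, before and after treatment: 2 × 121 = 242 to 2 × 146 = 292 microcuries for a participant who has both.
   - The DEXA table (component 2) discloses 6 mrem, while component 6 mentions no radiation.

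5. **Year-6 changes.** Section 6b, row 8, places dapagliflozin within pharmacological therapy. Neither drug table in Section 6c mentions dapagliflozin or the stopping of therapy.

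**The case against.** The strongest objection is that these are drafting slips in a form, and that the harms a reader might infer go beyond the documents. Much of that stands.

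- **Participants were misinformed.** A reader might infer that participants were told the experimental arm was guideline care, or that their open-label expectations were distorted. The documents do not show this. The consent form is not available, Section 4 labels the arms correctly, and it has the investigators explain the study in detail at interview.
- **Serious hypoglycemia on Group II therapy has no safeguard.** Not so. Section 7(1) asks about any potential risk, not only serious ones. Section 6a allows downward adjustment for glucose below 60 mg/dl and reviews home glucose results. Section 7 provides phone calls every two weeks after therapy starts, dose adjustment for severe side effects, and reporting of serious adverse events to the IRB within 24 hours. The gap is the severity entry and the clamp-only scope of Section 7(2).
- **Group II hypoglycemia is concealed.** It is not: it is listed as likely. The Background's remark that insulin raises the rate of hypoglycemia says nothing about severity and does not carry the point.
- **Every participant has two tracer infusions.** Section 10 pays participants with and without clamps separately, and Section 3 limits the hyperglycemic clamp to 50 of 720. The number having the euglycemic clamp is not clearly stated. Microcuries also cannot be set against the 6 mrem for DEXA, because the documents give no conversion. The tracer point is missing disclosure, not the size of the dose.
- **The sulfonylurea entries may be general exenatide text.** Possibly, but nothing marks them as not applying to Group I.

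The tick marks showing whether all groups are exposed are not legible for components 8 and 9. They could bear on the switched Group II participants, but each table names one group only.

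**Conclusion.** The point holds as a contradiction within the form, in five places: the arm named in Section 8, the serious column of component 9, the drugs in component 8, the tracer missing from component 6, and the missing entries for dapagliflozin and for stopping therapy. The first three are wrong or conflicting entries rather than mere lack of detail.

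The size is a count of mismatches. The only computed quantity is 121 to 146 microcuries per euglycemic clamp. It rests on the protocol's own formula and the assumed fasting glucose range, and it applies to clamp participants only.

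The conclusion does not extend to what participants were told or to an absence of hypoglycemia protection. It does not touch the HbA1c comparison, the endpoints or the sample size. The form should be corrected, because it bears on risk disclosure and the correction costs little.

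**What to change.** Amend the form as follows.

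1. In Section 8, change the arm described as following the ADA recommendations to Group II, and check that the consent form agrees.
2. In component 9, enter serious hypoglycemia in the serious column. Extend Section 7(2) beyond the clamp by referring to the safeguards already written in Sections 6a and 7.
3. Reconcile component 8 with the Group I regimen in Section 6a, for both the sulfonylurea entries and the missing insulin. State that the table's risks also apply to Group II participants switched to triple therapy at year 6.
4. In component 6, add the radiation exposure from tritiated glucose and say which participants it concerns.
5. Add risk entries for dapagliflozin and for the year-6 stopping of therapy. Since Section 6b already places dapagliflozin under pharmacological therapy, an added entry there may be enough in place of a new table.

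The cost is one amendment to the form and the consent wording. No treatment, visit, endpoint or analysis changes.
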